- 4) For women, negative pregnancy test and use of acceptable method of contraception.

Please note, because of the high incidence of depression that co-occurs with PTSD, those individuals with comorbid depressive disorders will be allowed into the study. This is in keeping with the purpose of this study to evaluate the effectiveness of a CPT in a “real world” clinical population. It also is anticipated that a significant proportion of Veterans and civilians will likely be treated with concurrent antidepressant pharmacotherapy [and/or with other medications (eg. prazosin).] However, again this enhances the “real world” application of treatments within the VA system, and secondly it is common to allow antidepressant medication in psychotherapy trials and still be able to show benefit with CPT.[37] For those who are already prescribed antidepressant medication, they will be continued on their current pharmacologic treatment Please note that since not all subjects will be on psychotropic medications, randomization will be stratified by presence of concurrent medications-a strategy we have used successfully in other comorbidity studies with PTSD[71]

Exclusion Criteria:

- 1) Females who are pregnant or lactating.
- 2) Veterans and civilians with a current unstable medical condition such as neurological, cardiovascular, endocrine, renal, liver, or thyroid pathology (e.g. abnormal BUN and creatinine, and unmanaged hypertension with BP > 200/120) which in the opinion of the physician would preclude the patient from fully cooperating or be of potential harm during the course of the study.
- 3) Veterans and civilians who meet current criteria for the following diagnoses (schizophrenia and schizophrenia spectrum and psychotic disorders) as determined by the MINI.
- 4) Veterans and civilians who have significant current suicidal or homicidal risks necessitating a higher level of care.
- 5) Those with known allergy or intolerance to buprenorphine.

Methods:

Overview: This study is a 14-week, RCT with open-label randomization to 2 groups (described in detail below): (a) buprenorphine (BUP) + CPT vs. (b) BUP + IDC. This study will be conducted in 3 Phases: Phase I:

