buprenorphine induction and stabilization for all participants (x1 week). Participants will be started at a dose of 2mg/0.5 mg BUP/NLX and this dose will be increased as needed for stabilization of opioid withdrawal symptoms up to 32 mg per day, which is standard practice. Phase II: randomization to CPT vs. IDC (x12 weeks). *CPT will be provided by one of our licensed therapists trained and who has been trained and certified in the standard VA rollout. The therapists will have weekly case consultation from a qualified CPT consultant. IDC will be provided by research staff under the supervision of [name]. All of the sessions will be recorded for supervision purposes and for the independent fidelity raters to assess 20% of the sessions for adherence and competence.** [Phase III: Subjects will be referred to one of the buprenorphine clinics (West Haven or Newington) and will be referred for ongoing treatment for PTSD if they choose, including the option for CPT for those who did not receive this during the study.]

Participants will be seen on a daily basis (excluding weekends) for the initial 5-7 day induction. Once subjects are on maintenance dose of BUP/NLX (goal is within 5 days), they will be seen weekly by study RN for the first 4 weeks, biweekly for a month then monthly for symptom evaluation, and medication refill.

[At study end, participants will be referred to a buprenorphine clinic. *Buprenorphine treatment is the standard treatment for OUD, and subjects who discontinue are at high risk for relapse.*]

* Due to COVID-19 precautions it may not be possible to record CPT/IDC sessions especially those conducted via telephone or telemedicine.

Main Outcome Measures: Symptoms of PTSD using the CAPS-5 and PCL-5. Frequency of opioid use using the TLFB and confirmed by urine toxicology. Other outcomes will include treatment retention measured by days in treatment and functioning using the VR-12. Functional impairment related to pain will be measured during the trial. Follow-up will be conducted at 1 and 3 months after end of the study to evaluate the durability of treatment effects on drug use and psychosocial outcomes.

To fully assess and appreciate complex symptomatology in this patient population, assessments were selected to have both relevance to our study of PTSD and comorbid OUD. Assessments will be done by an Independent Evaluator (IE) blind to treatment group.

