* Due to COVID-19 precautions it may not be possible to record CPT/IDC sessions especially those conducted via telephone or telemedicine.

Study Assessments:

Table 1: Summary of Study Assessments

Assessments	Baseline	1	2*	3*	4	5	6*	7	8	9	10	11	12	Follow Up 1 and 3 months*
CAPS	X								X					X X
PCL-5	X	X	X	X	X		X		X					X X
MINI	X													
TLFB	X	X	X	X	X		X		X					X X
DRRI-2	X													
Demographics	X													
COWS	X													
Blood Pressure/Pulse**	X	X	X	X	X		X		X					X X
Urine Toxicology**	X	X	X	X	X		X		X					X X
Pregnancy test (females)	X				X				X					X
PHQ-9	X	X	X	X	X		X		X					X X
ISI	X		X	X	X		X		X					X X
VR-12	X													X X
C-SSRS	X	X	X	X	X		X		X					X X
AE (SAFTEE)	X	X	X	X	X		X		X					X X
NRS for pain intensity	X				X				X					X
PROMIS-29	X				X				X					X
LEC-5	X													
CTQ	X													
Cannabis Use History	X													
Synthetic Cannabinoids Use History	X													

Note: Study visits occur weekly for 4 weeks, then biweekly, then monthly. Study assessments collected weekly are self-assessments and can be distributed and collected by the therapist conducting the therapy.

* In order to reduce the number of in-person visits weeks 2, 3, 6, and the two follow-ups (months 1 and 3) will be conducted via telephone or telemedicine.

** Due to COVID-19, blood pressure/pulse and urine toxicology will not be collected unless the visit is done in person.

COVID-19 Safety Precautions:

1. Adhere to local VA policies or mandates (ie., wearing cloth face coverings, COVID-19 screening at the main entrance, temperature checks, etc).
2. A study staff member will call participants the day before their scheduled visit and ask the COVID-19 screening questions; anyone who screens positive for COVID-19 (exposure or symptoms) will be rescheduled.
3. Staff members will sanitize high-touch surfaces before and after each in-person visit with approved disinfectant.
4. Staff members will wear protective facial masks, participate in frequent handwashing, and/or use alcohol-based hand sanitizer, and practice social distancing.
5. Only one participant will be scheduled for an in person visit at a time and visits will take place in a large enough space so that study staff and the participant can practice social distancing.
6. Contact information will be updated at each visit in the event that contact tracing needs to occur.
7. We will minimize the frequency and duration of study visits in the following ways:

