 - a. Attempt to schedule study visits on the same day as another clinic visit the patient has scheduled.
 - b. As much as possible, self-assessment forms should be completed via telephone or telemedicine and can be given directly or mailed to the participant in advance of any appointment. If the patient desires to complete in-person visit forms on site, staff will honor that request while maintaining social distancing.
 - c. Study therapy sessions (CPT or IDC) will be allowed to be conducted as telemedicine visits using VA approved platforms (e.g. VA Video Connect or VVC). If a video option is not possible, therapy can be conducted over the phone or in person (patient's choice).
 - d. Scheduled in-person visits at weeks 2, 3, 6, and the two follow-up visits (months 1 and 3) will now be conducted by telephone or telemedicine.

(a) **Clinician Administered PTSD Scale (CAPS-5)** will be used to diagnose PTSD and to obtain data [(pre and post treatment, follow-up)] on the frequency and severity of PTSD symptoms. The CAPS-5 is a structured diagnostic interview for DSM-5 diagnosis and the gold standard for assessing PTSD. It has excellent psychometric properties and diagnostic efficiency.[82] The CAPS for DSM-5[83] uses only a single 5-point ordinal rating scale to measure symptom severity. CAPS-5 scores range from 0 to 80 with higher scores indicating greater PTSD symptom severity. The CAPS-5 was revised with an eye towards maintaining backwards compatibility with the DSM-IV version of the instrument.

(b) **PCL-5** will be used to collect information on PTSD symptoms. The PTSD Checklist for DSM-5 [83] is similar in form to the PTSD Checklist (PCL) based on the DSM-IV.[84] The PCL-IV has excellent psychometric characteristics. The PCL-5 is a 20-item self-report measure, selected for its dimensional sensitivity, with higher scores reflecting greater PTSD severity. Scoring is based on how much the patient has been bothered by the symptoms on a scale from “0 = not at all” to “4 = extremely.” PCL scores will be collected based upon symptoms experienced in the past month at baseline, but since the last visit, during the weekly assessments.

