Study data will be collected and managed using REDCap electronic data capture tools hosted at VA CT Healthcare System. REDCap (Research Electronic Data Capture) is a secure, web-based application designed to support data capture for research studies, providing 1) an intuitive interface for validated data entry; 2) audit trails for tracking data manipulation and export procedures; 3) automated export procedures for seamless data downloads to common statistical packages; and 4) procedures for importing data from external sources.

Descriptive statistics and graphs will be used to summarize the data on all randomized subjects. All continuous variables will be examined for adherence to the normal distribution using normal probability plots and Shapiro-Wilk tests. Transformations will be applied if needed. If normality is not satisfied and transformations do not help with achieving normality alternative analytic strategies will be considered such as generalized estimating equations (GEE) or nonparametric methods for repeated measures analysis. Baseline demographic and clinical characteristics for the two randomized groups (e.g., age, gender, severity of PTSD, and opiate use) will be compared using chi-square tests for categorical variables and t-tests or nonparametric tests for continuous variables. If there are baseline differences between study treatment groups, these variables will be used as covariates in the mixed-effects models analyses described below. Drop outs and completers will also be compared on baseline characteristics using the same approach. Between group differences in treatment retention, medication compliance and frequency of the occurrence of side effect symptoms across the treatment period will also be assessed. Residual plots and other diagnostics will be used to assess model assumptions.

The primary analyses will be intent-to-treat but sensitivity analyses on completers and non-completers will also be performed. All statistical testing will be at a two-tailed alpha level of 0.05. *Adjustments for multiple comparisons will be conducted among measures in specific domains. In the case of PTSD symptoms (use of 2 measures, PCL-5 and CAPS-5) and opiate use (use of TLFB and urine toxicology) the level of significance will be adjusted to 0.025.*

Primary and Secondary Hypotheses:

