For the primary and secondary hypotheses, we will use mixed effects models to assess changes in PTSD symptoms and opiate use over time. Treatments will be used as between-subject factors and time (in weeks) will be used as a within-subject factor. The primary outcome variables will be PTSD symptoms as measured by generated from the PCL-5 and CAPS scales. The secondary outcome variables will be frequency of opiate use generated from the TLFB and confirmed with urine toxicology results each medication visit (weeks 1-4, 6, 8, 12) and follow-up. The use of the mixed-effects models approach for the analysis of our longitudinal data has several specific advantages. Unlike traditional repeated measures analyses, mixed effects models allow for different numbers of observations per subject, use all available data on each subject and are unaffected by randomly missing data. They also provide flexibility in modeling the correlation structure of the data.[96]

Primary Aim 1. We hypothesize that CPT will significantly reduce PTSD symptoms compared to IDC in Veterans and civilians with PTSD and comorbid OUD maintained on buprenorphine.

This hypothesis will be tested by the interaction of treatment (CPT vs. IDC), and time in the mixed model specified above. Significantly greater decrease in PTSD symptoms in the CPT group will be considered supportive of the hypothesis.

Secondary Aim 1. We hypothesize that CPT will significantly reduce opioid use compared to IDC in Veterans and civilians with PTSD and comorbid OUD maintained on buprenorphine.

This hypothesis will be tested by the same approach as described in primary aim 1 but with frequency of opioid use as the dependent measure.

Exploratory Hypothesis:

We hypothesize that CPT will significantly improve retention (days in treatment) compared to IDC in Veterans and civilians with PTSD and comorbid OUD maintained on buprenorphine.

This hypothesis will be tested using ANOVA or nonparametric equivalent comparing the two treatment groups (CPT vs. IDC).

We hypothesize that CPT will significantly improve psychosocial functioning (measured by the VR-12 survey) compared to standard counseling in Veterans and civilians with PTSD and comorbid OUD maintained on buprenorphine.

This hypothesis will be tested by the interaction of treatment (CPT vs. IDC) and time.

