c) Subjects who are randomized to Individual Drug Counseling (IDC) will receive 12 weeks of therapy by a licensed provider. IDC uses a semi-structured, time-limited addictions-counseling model. The main focus is on helping individuals achieve and maintain abstinence by encouraging behavioral changes, such as avoiding triggers, structuring one's life, and engaging in healthy behaviors (e.g., exercise). The current standard of treatment for individuals entering buprenorphine maintenance is to do drug counseling. In most VA settings, including VA Connecticut Healthcare System, psychiatric symptoms (such as PTSD) are evaluated but psychiatric treatment is often deferred until the individual demonstrates a commitment to treatment and demonstrates abstinence. Standard counseling is the primary means to achieve these goals. PTSD symptoms are not addressed and this may lead to worsening of PTSD symptoms. In cases where worsening of PTSD symptoms necessitates a change in case, the same strategies (outlined later in this document) will be used across treatment conditions.

d) Nonspecific Risks: Other risks from the counseling, rating scales and urine collections are not beyond usual clinical procedures in a substance abuse treatment program. Confidentiality of study results are specifically protected by Federal laws, and all records will be identified by code number only, with the master file kept under lock by the Principal Investigator or Data Manager. With the handling of medical and research records, there is always the possibility of a breach of confidentiality.

- **Sources of Materials:** Sources of research material include interview assessments conducted by trained Independent Evaluators, self-reported questionnaires, medical record review, urine samples, activity patterns, sleep patterns, etc. that will be obtained specifically for research purposes.
- **Therapeutic risk:** All subjects will be inducted into buprenorphine maintenance, the risks of which are described above.
- **Research risk:** The research risks include the risks of the interventions into which subjects will be randomized, and include CPT and standard counseling, all of which are described above. In addition, there are risks associated with gathering of assessments, and a potential breach of confidentiality. These have also been described above.

Adequacy of Protection from Risk

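### The Table 1 note lets the treating therapist hand out and collect the PCL-5, a primary self-report outcome in an open-label trial; a non-therapist should do this in both arms, and the plan should say whether blinding covers the form

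*Combined protocol and SAP*

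**What the plan says.** All of these are in section 6 (Research Plan) of the combined protocol and SAP.

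- **Design** (Methods, Overview): "This study is a 14-week, RCT with open-label randomization to 2 groups". Participants and therapists know the arm.
- **Assessor** (end of the Main Outcome Measures text, which names the CAPS-5 and PCL-5): "Assessments will be done by an Independent Evaluator (IE) blind to treatment group". No measure is excepted.
- **Form handling** (note under Table 1): "Study assessments collected weekly are self-assessments and can be distributed and collected by the therapist conducting the therapy".
- **Type of measure** (Study Assessments, item b): "The PCL-5 is a 20-item self-report measure". The same item places it among the weekly assessments.
- **Status** (Data Analysis, Primary and Secondary Hypotheses): "The primary outcome variables will be PTSD symptoms as measured by generated from the PCL-5 and CAPS scales". For the pair of PTSD measures, "the level of significance will be adjusted to 0.025".
- **Control arm** (Potential Risks, item c): "PTSD symptoms are not addressed and this may lead to worsening of PTSD symptoms".
- **Data sources** (Sources of Materials): interviews by Independent Evaluators and self-reported questionnaires are listed as separate items. Who handles the questionnaires is not stated.

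**The concern.** With a self-report outcome in an open-label trial, some expectancy bias is unavoidable, because participants know what they are receiving. The Table 1 note may add a component that can be avoided. In the CPT arm the person who takes back the PTSD form may be the person treating the PTSD. In the IDC arm the collector may be a drug counsellor, whose work is not aimed at those symptoms. One collection rule thus creates a different social situation in each arm. Participants might understate symptoms to please the therapist, or overstate them to show need; the documents do not tell us which, if either.

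At stake is the PCL-5 treatment-by-time test, which is one of the two primary tests of Primary Aim 1.

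**Working it through.** The point rests on the text, so the first four steps compare passages. Step 5 is an illustration only.

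1. **Does the note reach the PCL-5?** Yes. It covers self-assessments collected weekly, and Study Assessments item b makes the PCL-5 a self-report taken at the weekly assessments.

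2. **Which visits does it reach?** This is unclear. Read strictly, weekly means weeks 1 to 4, because the same note says visits then become biweekly and monthly. But item h says the PHQ-9 is collected weekly, and Table 1 ticks the PHQ-9 at the same visits as the PCL-5, including weeks 6 and 8. Later visits may therefore be covered too.

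3. **Does it contradict the blind-evaluator sentence?** Two readings are possible.
   - The sentence covers every assessment. Then the note conflicts with it, since a therapist delivering the treatment cannot be blind to it.
   - The sentence covers interviews only, as Sources of Materials suggests. Then there is no conflict, but a primary outcome sits outside the blinding and the plan does not say so.

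   No passage chooses between them. One clarifying sentence is needed on either reading.

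4. **Is a comparable collector available?** Yes. Nurse-led Medical Management is given to all participants at each visit. The nurse sees them weekly for 4 weeks, biweekly for a month, then monthly (Standard Treatment, Buprenorphine). This fits the medication visits at weeks 1-4, 6, 8 and 12 in Data Analysis. COVID-19 Safety Precautions item 7b already allows telephone, telemedicine and mailed forms.

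5. **Illustration only: why the visits need to be named.** The documents give no size for a reporting shift, so every shift and correlation here is assumed.
   - *Inputs.* From the plan: 60 per arm (Power analysis), two-sided 0.025, baseline plus weeks 1, 2, 3, 4, 6, 8, 12. Assumed: SD 1, no missing data, no true effect, a shift δ = 0.2 SD towards CPT, and correlation R either constant at 0.5 or 0.7, or decaying to 0.5 or 0.7 per 4 weeks.
   - *Formula.* With X = [1, t] and s the vector of shifts, the slope bias b is the second element of (X′R⁻¹X)⁻¹X′R⁻¹s. SE = √{(2/60)·[(X′R⁻¹X)⁻¹]₂₂}. P(false CPT win) = Φ(b/SE − 2.241), and P(false IDC win) = Φ(−b/SE − 2.241). Each is 1.25% when b = 0.
   - *Shift at all post-baseline visits.* With constant correlation 0.5, b = 0.00804 per week and SE = 0.01220, so b/SE = 0.659 and Φ(0.659 − 2.241) = 5.7%. Across the four correlations the false CPT win is 5.7% to 9.2%.
   - *Shift at weeks 1-4 only.* With constant correlation 0.5, b = −0.01429 and b/SE = −1.171, so the false **IDC** win is Φ(1.171 − 2.241) = 14.2%. Across the four correlations it is 1.5% to 23.3%. An early shift towards CPT flattens the later CPT slope, so the error goes against CPT.
   - *Categorical time.* The plan says "Treatments will be used as between-subject factors and time (in weeks) will be used as a within-subject factor" and does not fix how time is modelled. With an omnibus 7-df interaction test (nominal 2.5%), rejection is about 9% to 34% for all visits and 21% to 52% for weeks 1-4.

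   A shift of the opposite sign reverses the direction of the linear results. The figures show only that the result depends on which visits are affected and how time is modelled. They do not measure any bias in this trial.

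**The case against.** The strongest reply is that nothing here conflicts. A participant completes a self-report form, so an evaluator does not conduct it as an interview, and handing a form over and taking it back is not assessing. Sources of Materials keeps evaluator interviews and questionnaires apart. This is the likelier reading. It removes any claim of a plain contradiction, but it leaves the PCL-5 outside the blinding without acknowledgement.

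Second, the note is permissive. It does not say that the therapist reads, scores or discusses the form, and item 7b steers self-assessments towards telephone or telemedicine. This stands: how often therapists handle the form is unknown.

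Third, the CAPS-5 is itself primary and is assigned to a blind evaluator, and Primary Aim 1 presents it as confirming the PCL-5. That is real protection for the trial's conclusion, but not for the PCL-5 test.

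Fourth, participants would still know their arm after the change, and no passage says that the nurse is blind. This also stands and limits what the fix can claim.

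A reader might infer that the arrangement favours CPT, or that the PCL-5 result is compromised. The documents support neither. They give no size, direction or frequency, and even under an assumed shift towards CPT the linear test can err in either direction.

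**Conclusion.** The point holds as a cheap improvement. The plan expressly permits the unblinded treating therapist to distribute and collect a primary self-report outcome. It does not say whether its blind-evaluator sentence covers that outcome, or which visits the permission covers. A reporting bias that differs by arm is possible and avoidable; its size and direction are unknown and it could be zero.

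The conclusion rests on the wording alone: the note includes the PCL-5, the PCL-5 is primary, the trial is open-label, and the two therapies differ in whether they address PTSD. It does not rest on the illustrative percentages. Sample size, alpha and power are unaffected.

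**What to change.** 1. After the blind-evaluator sentence, state whether it covers the PCL-5 or only the interviews. If only the interviews, say that the PCL-5 is an unblinded self-report.

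2. Amend the Table 1 note along these lines: *At every visit, the PCL-5 used as a trial outcome is distributed and collected by the study nurse or other non-therapist research staff, in person, by telephone or telemedicine, or by mail. The treating CPT or IDC therapist does not distribute or collect it.*

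3. Apply this in both arms from one date, and record who collected each PCL-5 from then on.

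4. Leave the C-SSRS, the PHQ-9 and the therapists' monitoring of distress (Protection Against Risk) unchanged.

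5. Optional: where the collector of earlier forms is known, repeat the PCL-5 analysis without therapist-collected forms. No passage says that such records exist. The exclusion may also be selective, because therapist collection can track therapy attendance.

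**Cost.** A small workflow change using visits already planned; the documents do not give the nurse's workload. Therapists would no longer receive the form directly. If the change comes mid-trial, handling may differ before and after the date, which is why both arms should switch together. The gain is the same kind of non-treating collector in both arms, not a blinded one.
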